There is additional support for the analgesic properties of vibratory stimulation outside of the facial plastic surgery literature. A systematic review evaluated evidence of the effectiveness of vibratory stimulation to reduce needle-related procedural pain in children.²⁰ The meta-analysis of this systematic review showed

that vibratory stimulation was significantly effective according to both self-rated and observer-rated pain measurements regardless of age group, type of procedure, or type of vibration device.²⁰ Within the dermatology literature further support can be found. Park et al. studied VAS scores when vibration anesthesia was used during keloid triamcinolone injections. Intralesional injection therapy without vibration yielded mean VAS scores of 59 compared to 33 when vibration was used (P < .05).²⁷ Fix et al. studied vibration anesthesia during the injection of lidocaine in an open label, randomized, controlled, split-body trial. The median VAS pain score was 26 for injections without vibration versus 7.5 with vibration (P<0.01).²⁸

However, no study to date has analyzed the use of vibration analgesia during VFI.

Study Design and Methods

Methods: Describe in lay terms, completely detailing the research activities that will be conducted by Mayo Clinic staff under this protocol.

Each patient will undergo each of the three treatment modalities. The order in which they receive these will be randomized.

Treatment Group A (control): No anesthesia

Treatment Group B: 0.5cc subcutaneous 2% lidocaine in 1:100,000 epinephrine (done approximately 2 minutes before Botox injection)

Treatment Group C: Vibrating instrument held adjacent to cricothyroid space as Botox injection is performed

The nurse assisting the procedure will also time the Botox portion of the procedure to enable analysis of whether pain is associated with longer procedure time.

Patient participation is expected to last approximately 6-12 months. The study specific questionnaire #1 will be given at only their first visit. Study specific questionnaire #2 will be given immediately after each Botox injection.

Subject Information

Target accrual is the proposed total number of subjects to be included in this study at Mayo Clinic. A "Subject" may include medical records, images, or specimens generated at Mayo Clinic and/or received from external sources.

Target accrual: 50

Subject population (children, adults, groups): Adults with spasmodic dysphonia

Inclusion Criteria:

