🗌 Data	Specimens Data & Specimens	
🗌 Data	Specimens Data & Specimens	
🗌 Data	Specimens Data & Specimens	

Data Analysis

Power analyses may not be appropriate if this is a feasibility or pilot study, but end-point analysis plans are always appropriate even if only exploratory. Provide all information requested below, or provide justification if not including all of the information.

Power Statement:

Sample size estimation is estimated based on the repeated methodology; that is, the VAS score will be measured at three time points (initial visit, 3 months and 6 months) for each patient. The comparisons between treatment arms (treatment B and C) and control arm (A) are of interest. To preserve the family wise type I error rate, 0.05, Bonferroni approach is used to adjust the pairwise type I error (0.05/2 = 0.025). We further assume the standard deviation across subjects at the same time point is 3.00, and there is a weak correlation between the VAS (<= 0.3) within each patient. To achieve 80% to detect statistically significant differences in the mean VAS between A and B, and between A and C, the required sample size based on different value of correlation are listed below:

VAS			Required sample size		
Α	В	С	Correlation $= 0.3$	Correlation $= 0.1$	Correlation =
					0.05
4	1	1	18	21	22

	2	2	32	40	42
	3	3	114	145	153
5	2	2	18	31	22
	3	3	33	40	42
	4	4	114	145	153
6	2	2	13	14	14
	3	3	18	21	22
	4	4	32	40	42
	5	5	114	145	153

Note: The weaker the correlation and the smaller the mean difference in VAS the larger the sample size. Randomization schedule will be generated by the study statistician. Randomization will determine the order they get these treatments and can follow any permutation.

Data Analysis Plan:

Data Handling

The study data will be entered and saved in REDCap. The REDCap database will be created by the study personnel. Only the PI and study personnel will have access to the database. Data analysis

Data will be summarized by mean (standard deviation) or median (interquartile range) for continuous variables, and frequency count (percentage) for categorical variable. The number of patients without the VAS score at 3- and 6-months after the initial visit will be reported. Generalized estimating equation will be used to compare the mean VAS score between groups, and the point estimate of the mean difference and 95% confidence interval will be reported.

Endpoints

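### Does the GEE for the primary VAS comparison need a named visit term?

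*Combined protocol and SAP*

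**What the plan says.** Under Study Design and Methods: "Each patient will undergo each of the three treatment modalities. The order in which they receive these will be randomized". The pain questionnaire follows every treatment: "Study specific questionnaire #2 will be given immediately after each Botox injection". The Power Statement fixes the schedule, saying that "the VAS score will be measured at three time points (initial visit, 3 months and 6 months) for each patient", and leaves the order open: "Randomization will determine the order they get these treatments and can follow any permutation". The study statistician prepares the schedule; neither blocking nor simple randomisation is mentioned. Subject Information gives "Target accrual: 50".

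The model itself has one sentence, under Data Analysis Plan: "Generalized estimating equation will be used to compare the mean VAS score between groups, and the point estimate of the mean difference" and its 95% confidence interval are to be reported. Visit, period and sequence are neither included nor excluded, there or elsewhere. On variability, the Power Statement says: "We further assume the standard deviation across subjects at the same time point is 3.00", with a within-patient correlation of at most 0.3 and a pairwise alpha of 0.025.

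**The concern.** In a three-period crossover, visit is a design factor crossed with treatment, and a period term is routine. The plan's sentence is short enough that two analysts could follow it and fit different models. If pain rises or falls over successive injections in all patients, a model without visit leaves that change in the within-patient differences. With unrestricted orders, B minus A and C minus A then become noisier. With balanced orders the estimates are unharmed, but the reported standard error is too large and the test is conservative.

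The wording of the planning SD seems to point the same way: an SD taken at one time point excludes movement between visits, so a model with visit might look like the one the sample size was built for. At stake would be power for the two primary comparisons and the width of their confidence intervals.

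**Working it through.** **Inputs.** From the Power Statement: SD 3.00 (variance 9), correlation ρ of 0.05, 0.1 or 0.3, pairwise alpha 0.025 (taken as two-sided, z = 2.241), three visits. From Subject Information: n = 50. Assumed, because the plan does not give them: complete data, any shift in pain between visits, and a 2-point target difference (the table lists differences of 1 to 4 points and names no target).

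**The plan's own table.** A one-group repeated-measures Hotelling T² test at alpha 0.025 and 80% power needs, for ρ = 0.3 / 0.1 / 0.05:

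- 1 point: 113 / 144 / 152 (plan 114 / 145 / 153)
- 2 points: 31 / 39 / 41 (plan 32 or 33 / 40 / 42)
- 3 points: 16 / 20 / 21 (plan 18 / 21 / 22)
- 4 points: 11 / 13 / 14 (plan 13 / 14 / 14)

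All cells agree within 2 patients except the 5/2/2 row at ρ = 0.1, which prints 31 where the other 3-point rows print 21. That looks like a slip and has no bearing here. The calculation contains no visit effect.

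**Variance without visit.** With complete data the GEE contrast is the mean within-patient difference. Suppose pain shifts linearly by g points per visit. Over the six orders, the signed visit gap between two treatments is ±1 in four orders and ±2 in two. Its mean is 0, so there is no bias, and its mean square is (4×1 + 2×4)/6 = 2. Hence

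V₀ = (1/n)[18(1−ρ) + 2g²] = (2/n)[9(1−ρ) + g²].

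**Variance with categorical visit, unrestricted orders.** V₁ = (2/n)·9(1−ρ)·(1 + c), where c reflects chance imbalance of treatments over visits. It is roughly 1/n = 2.0%; inverting the information matrix over simulated order lists gives about 2.1%.

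**Break-even.** Setting V₀ = V₁ gives g = √[c·9(1−ρ)]:

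- ρ = 0.05: √(0.021 × 8.55) = 0.42
- ρ = 0.1: √(0.021 × 8.10) = 0.41
- ρ = 0.3: √(0.021 × 6.30) = 0.36

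For a single step s after visit 1, two treatments straddle the step in two thirds of orders, so 2g² becomes (2/3)s². The break-even is √3 times larger: 0.63 to 0.73 point.

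**Power for a 2-point difference**, Φ(2/√V − 2.241):

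| Shift per visit | ρ | V₀ | V₁ | V₀/V₁ | Power without | Power with |
|---|---|---|---|---|---|---|
| 0 | 0.05 | 0.342 | 0.349 | 0.98 | 0.881 | 0.874 |
| 0 | 0.3 | 0.252 | 0.257 | 0.98 | 0.959 | 0.956 |
| 0.5 | 0.05 | 0.352 | 0.349 | 1.01 | 0.871 | 0.874 |
| 0.5 | 0.3 | 0.262 | 0.257 | 1.02 | 0.952 | 0.956 |
| 1 | 0.05 | 0.382 | 0.349 | 1.09 | 0.840 | 0.874 |
| 1 | 0.3 | 0.292 | 0.257 | 1.13 | 0.928 | 0.956 |

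**Simulation check.** A simulated crossover (exchangeable working correlation, robust SE, t on n−1 df) gives the same variance ratios within about 0.01. At 1 point per visit, power without against with visit is 0.825 against 0.863 at ρ = 0.05 and 0.916 against 0.947 at ρ = 0.3. Null rejection at nominal 2.5% is 2.3–2.6% without visit and 2.5–2.8% with it. With visit, the robust SE is slightly too small at n = 50 (0.581 against a true 0.590 at ρ = 0.05), so simulated power flatters that model and the variance ratio is the fairer comparison.

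**Balanced orders (blocks of six).** Here c falls to about 0.1%, and the true variances with and without visit agree closely. Without visit, the reported SE is too large by √[1 + g²/(9(1−ρ))]. At g = 1 this is √(9.55/8.55) = 1.057 at ρ = 0.05 and √(7.3/6.3) = 1.076 at ρ = 0.3. Simulated null rejection is then about 1.7–2.0%, which errs on the safe side.

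**The case for a change.** The best case for a change is that the trade is lopsided. With no shift, the visit term costs less than 1 percentage point of power; with 1 point per visit, omitting it costs about 3 to 4. If the statistician blocks the orders, the term is almost free and corrects an overstated SE. Visit is already known for every score, and stating the model beforehand removes a later choice between two fits.

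Much of this stands. The sentence is incomplete, the term is cheap, and an analyst who includes it, particularly under blocked orders and with a small-sample correction to the robust SE, is acting well. But the upside rests on a shift that the documents neither give nor suggest. On the plan's own inputs, with unrestricted orders, the larger model is slightly worse.

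The planning SD does not settle it. Since order is randomised, patients seen at one visit are on different treatments, so that wording cannot be read literally as the residual SD of a visit-adjusted model. The table is reproduced by a calculation with no visit effect. With no shift, V₀ equals the planning variance and V₁ lies about 2% above it.

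**Conclusion.** No change follows. The plan leaves open a modelling detail that an analyst can fill sensibly either way, and both fits are consistent with its GEE sentence. With randomised order and complete data, neither choice biases B minus A or C minus A, and omitting visit does not inflate type I error.

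The difference is about 2% in variance against a visit term when there is no shift, nil near 0.4 point per visit, and 9% to 13% in its favour at 1 point per visit. For a 2-point difference the largest loss considered, at 1 point per visit, leaves power above 80%. For a 1-point difference the trial is underpowered under either model, since the table asks for 114 to 153 patients.

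The 2% and 0.4-point figures assume n = 50, SD 3, unrestricted orders, a linear shift and complete data. With blocked orders the threshold disappears, and omission only makes the test somewhat conservative if pain shifts. Evidence of a consistent change in pain of about 1 point or more between visits would strengthen the case for naming the term; the documents contain none.
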